**Study Protocol: Emotion-Diet Interactions in Pregnancy**

**NCT04430439**

**Date of Document: 10/20/2022**

**C.1 Overview.** This research will represent the first investigation of objectively measured diet-stress interactions in human pregnancy, thus providing critical insight to the contribution of psychosocial stress in influencing important gestational metabolic pathways that have implications for maternal and child health and disease risk. The working hypothesis is that acute psychosocial stress will exacerbate the postprandial plasma glucose/insulin and free fatty acid (FFA) response to a standardized meal, and that this response will be exaggerated after consumption of a high GI versus a low GI meal. The overall strategy is to enroll a cohort of non-diabetic pregnant women with overweight and obesity to test the postprandial metabolic response to a standardized meal of varying GI, with and without psychosocial stress exposure.

**C.2 Study Design.** This is a two-armed, randomized, cross-over study in which N=80 women will be randomly assigned in a parallel design to either a low or high GI standardized breakfast. Within each arm, N=40 women will attend two test study visits in a randomized, cross-over design, to undergo either the TSST challenge task or a control non-stress task immediately following consumption of their assigned meal type.

**C.3 Clinical Research Setting.** The study will be performed at the PI's research facility on the UCI campus in Irvine and will utilize additional clinical facilities of the UCI Institute of Clinical and Translational Science (ICTS).

**C.4 Study Site and Population.** Subjects will be primarily recruited from UCI-affiliated clinics; the UCI Medical Center faculty private practice, and UCI-affiliated family health clinics in surrounding districts within Orange County, CA, which serve women from an urban metropolitan area encompassing a population base of over 2.75 million residents. Recent demographic profiles of this population indicate that 68% of the patients are multiparous; 65% are married, and 58% belong to ethnic minority groups (predominantly Hispanic). Over the past year, the PI has independently enrolled N=33 Hispanic women from this prenatal population.

#### **C.5 Subjects and Recruitment**

**C.5.1 Selection Criteria:** *Inclusion criteria:* a)  $\leq 22$  week's gestation at recruitment, b)  $> 18$  years age, c) singleton intrauterine pregnancy, d) non-smoker, e) pre- or early-pregnancy BMI  $25.0-39.9$  kg/m $^2$ , f) non-diabetic. *Exclusion criteria:* a) presence of any prior and present obstetric risk conditions such as placental or cord abnormalities, uterine anomalies, congenital malformations, fetal chromosomal abnormalities, infection, diabetes, hypertension, b) psychiatric disorders such as clinical depression or PTSD, c) any conditions that may dysregulate neuroendocrine, metabolic or cardiovascular function, such as diabetes, hepatic, renal, or autoimmune disorders, d) use of lipid-lowering or anti-diabetic medications, e) use of corticosteroids in the last month or any prior use of psychotropic medications, f) current smoker or use of tobacco products within 1 year prior to pregnancy, g) current or history of alcohol abuse or illicit drug use, h) pre- or early-pregnancy BMI  $< 25.0$  or  $\geq 35.0$  kg/m $^2$ .

**C.5.2 Participant Recruitment:** Pregnant women will be actively recruited from UCI-affiliated prenatal clinics. A partial waiver of HIPAA will be requested to review the appointment lists and screen the electronic medical record for potential eligibility. Potential participants will be explained the study, provided written study information and invited to participate. The recruitment strategy will be supplemented by passive methods involving IRB-approved mass media announcements through UCI resources (flyers, employee-wide emails and online media advertisements). All disseminated study advertisement material will include the PI's name and contact information, enabling interested and potentially eligible pregnant women to enquire for further details and eligibility screening. All recruited study participants will provide informed signed consent at the first study (screening) visit.

#### **C.6 Visit Protocols and Study Measures.**

**C.6.1 Screening & consent visit:** This visit will entail informed consent and confirmation of full study eligibility in order to proceed with subsequent test visits. An interview with a trained research coordinator will determine whether any medical conditions, psychiatric disorders or medication usage may render them ineligible to continue participation. Peripheral blood glucose will be tested by glucometer to detect potential undiagnosed diabetes (random glucose  $\geq 200$  mg/dl). Those considered eligible to continue participation will be provided instructions to complete an online survey at home before their first test study visit. This will assess maternal sociodemographic factors, psychosocial states (e.g. chronic stress, anxiety, resiliency) and behaviors (e.g. usual dietary intake, sleep, exercise habits). A standardized healthy evening meal of medium GI will be delivered to participant homes prior to each test study visit to control for recent dietary influences on morning glycemia.

**C.6.2 Test visit 1:** Participants will attend the research lab facility in the morning following an overnight fast (minimum 8 hours), between 20-22 week's gestation. A research nurse will place an indwelling catheter to the antecubital vein to allow frequent blood sampling throughout the test period with minimal discomfort. After catheter placement, women will rest comfortably for 30 mins. A fasting blood and saliva sample will be collected immediately prior to consumption of the assigned standardized breakfast meal, followed by performance of either the psychosocial stress or non-stress protocol. Postprandial blood and saliva samples will be collected at +30 (pre-task), 45 (post-task), 60, 75, 90, 120 & 150 mins. A heart rate variability monitor will be worn throughout the

duration of each test study visit. Immediately pre- and post-task protocols, participants will complete questionnaires to assess momentary affective state and self-appraisal of upcoming/completed tasks.

**C.6.3 Test visit 2:** All participants will be allowed a 1-week “wash-out” period before returning to the research lab for test visit 2. Participants will undergo the same protocol as test visit 1 with the same meal assignment, except with the alternative stress/non-stress paradigm as performed on visit 1.

**C.6.4 Experimental stress/non-stress paradigm:** The TSST is a standardized, validated experimental procedure to effectively induce psychosocial stress among healthy adults, including pregnant women. The TSST takes 15 mins to complete and involves a 5 min speech preparation, 5 min speech performance under stern observation of an evaluative committee while being video-taped, and 5min complex verbal arithmetic task. For the control non-stress condition, women will have a relaxed 15 min conversation with a familiar researcher.

**C.6.5 Test meal composition:** Test meals will be prepared by research staff under direction of the study PI, a registered dietitian. Both types of test meals will have comparable caloric content but will vary in fiber, carbohydrate and fat content to alter the GI value (*Table 1*). The pre-visit standard evening meals will have a medium GI value. All participants will be asked about food allergies or intolerances and the meals will be adapted as appropriate, while maintaining an equivalent energy content and macronutrient distribution.

**Table 1:** approximate nutritional composition of standard evening and test visit meals

	Standard pre-visit evening meal	Low GI test meal	High GI test meal
Energy, kcal	600	300	300
% carbohydrate	55	47	76
% protein	15	19	13
% fat	30	33	12
Fiber, g	15	4.5	0.7

**C.6.6 Bio-sample processing and analysis:** Fasting and postprandial blood samples will be centrifuged at 1500rpm for 15min and the separated plasma aliquoted to microtubes. All plasma and saliva will be stored at -80°C until analysis. Plasma will be assayed for glucose and insulin and saliva for cortisol by ELISA. Plasma FFA will be measured by LC-MS/MS. HOMA-IR will be computed from fasting glucose and insulin values and Adipo-IR from fasting insulin and FFA values. The AUCglu/ins and AUCFFA will be determined for each visit.

**C.6.7 Randomization procedures:** A biostatistician will generate the randomization sequence for a 1:1 assignment to the meal group arms (*i.e.* high GI or low GI), and for the sequence of stress or non-stress protocols at the test study visits (*i.e.* stress at v1 and non-stress at v2, or non-stress at v1 and stress at v2) within each arm. Randomization sequences will be contained in sealed, opaque envelopes labeled by sequential study IDs and only revealed by research coordinators after completion of a screening visit for a fully eligible participant.

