Statistical Analysis Plan: Emotion-Diet Interactions in Pregnancy (PREDIP)

NCT04430439

Date of document: 4/6/2020

STATISTICAL DESIGN AND POWER ANALYSIS

Statistical Design: The statistical approach for each of the Specific Aims will be performed as follows:

Aim 1a: A cross-over study design will test the hypothesis that experimental exposure to a standardized psychosocial stress task will potentiate the postprandial metabolic response to the standardized meal. Each subject will represent her own control within the assigned meal group (low or high GI). A paired-samples t-test will be employed, using the model: $E[Y_i] = \Delta AUC_i = (AUC_i)v1 - (AUC_i)v2$

where Y_i denotes the outcome measurement (change in $AUC_{glu/ins}$ or AUC_{FFA}) on maternal i, and AUC_i denotes the AUC for either metabolic outcome at a given laboratory visit; v1 or v2. As such, a test of the hypothesis that the above equations equals 0, represents a test that the effect of acute psychosocial stress exposure does not moderate the postprandial response to a standardized meal. A sensitivity analysis to estimate the difference in response by randomization sequence will ensure that the order of protocols does not confound the results.

Aim 1b: To explore the difference in the postprandial metabolic response following acute psychosocial stress exposure across meal types (low vs high GI), an independent sample t-test will be employed to compare the mean $AUC_{glucose/insulin}$ between the high GI and low GI groups.

Aim 2: To determine whether individual variation in biological stress reactivity (i.e., $AUC_{cortisol}$ and AUC_{HRV}) moderates the effect of acute psychosocial stress on the metabolic response to the standardized meal, a general linear model accounting for within subject correlation will be employed, according to the model:

$$E[Y_{ij}] = \beta_0 + \beta_1 STRESS_{ij} + \beta_2 REACT_{ij}$$

where Y_{ij} denotes the outcome change in the AUC_i on maternal i, STRESS denotes the condition of exposure (stress vs no stress) to mother i on laboratory visit j, and REACT denotes stress reactivity, measured by $AUC_{cortisol}$ or AUC_{HRV} . A test of $H_0: \beta_1 = 0$ will test the hypothesis that mean AUC_i ($AUC_{glu/ins}$ and AUC_{FFA}) differs by stress condition after adjustment for stress reactivity. An exchangeable correlation matrix will be assumed in the model.

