Power Analysis: The primary outcome of the proposed research is the difference in the postprandial glucose/insulin response to a standardized meal (of either low or high GI) between the stress and non-stress conditions. Utilizing a cohort of 40 women in each meal group, it is estimated that the proposed study will have approximately 80% power to detect a 0.44 standard deviation difference in the mean within subject change in postprandial metabolic response ($AUC_{glu/ins}$ and AUC_{FFA}), associated with the introduction of the stress paradigm.

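### The AUC for the stress contrast has no stated window or type and makes no use of the pre-task samples; on a total AUC over 0-150 min those samples cost precision, not validity

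*Protocol*

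**What the plan says.** Protocol C.6.2 sets the order of events at each test visit. "A fasting blood and saliva sample will be collected immediately prior to consumption of the assigned standardized breakfast meal". Then: "Postprandial blood and saliva samples will be collected at +30 (pre-task), 45 (post-task), 60, 75, 90, 120 & 150 mins". C.6.4 adds that "The TSST takes 15 mins to complete", which fits the slot between +30 and +45.

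The outcome is described only briefly. C.6.6 says that the glucose/insulin and FFA AUCs "will be determined for each visit". In the SAP, under Aim 1a, AUC_i "denotes the AUC for either metabolic outcome at a given laboratory visit; v1 or v2". Neither document gives a start, an end, an integration rule, a choice between total and incremental AUC, or any adjustment for the fasting or +30 values. The only sensitivity analysis named in the SAP concerns randomisation sequence.

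The AUC feeds the main comparison. The SAP states that "The primary outcome of the proposed research is the difference in the postprandial glucose/insulin response to a standardized meal" between the stress and non-stress conditions, and for Aim 1a that "A paired-samples t-test will be employed".

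C.2 describes the timing differently. There, women attend "to undergo either the TSST challenge task or a control non-stress task immediately following consumption of their assigned meal type", with no mention of a 30-minute interval or a pre-task sample.

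**The concern.** The randomised contrast is stress against non-stress. On the C.6.2 schedule the fasting and +30 samples are drawn before that exposure starts. Apart from anticipation, a difference between visits at those times reflects only the woman's day-to-day variation in fasting state and early meal response. A total AUC from time zero adds that variation to the outcome without adding expected signal.

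The same samples could instead be used to remove noise, because a woman who runs high before the task on one day is likely to run high after it. The plan collects what it needs for this and gives it no role in the metabolic analysis.

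Three things are at stake. One is precision in a comparison planned at about 80% power with 40 women per meal group. Another is freedom to choose the AUC window and type after the data are seen. The third is the meaning of the 0.44 SD in the power statement, which depends on which AUC is meant.

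**Working it through.** **Inputs.** Sampling times 0, 30, 45, 60, 75, 90, 120, 150 min (C.6.2); task of 15 min (C.6.4); 40 women per meal group, 0.44 SD, about 80% power (SAP, Power Analysis). Alpha and sidedness are not stated; 0.05 two-sided is assumed. Variances, correlations and the shape of the stress effect are not given and are assumed below.

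**1. The plan's own figure.** For a paired test by normal approximation, power = Φ(0.44 × √40 − 1.960) = Φ(2.783 − 1.960) = Φ(0.823) = 0.795. The stated 80% is reproduced (0.774 with the noncentral t).

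**2. Trapezoid weights, total AUC 0-150.** Each sample's weight is half the sum of its adjacent intervals: 15, 22.5, 15, 15, 15, 22.5, 30, 15; sum 150.
- Fasting and +30 together: (15 + 22.5)/150 = 25%.
- Pre-task time: 30/150 = 20%. The two figures differ because 7.5 of the +30 weight belongs to the 30-45 min interval.
- For AUC 30-150, the +30 sample carries 7.5/120 = 6.25%.
- For an incremental AUC (total minus fasting × 150), the fasting weight is 15 − 150 = −135, and the 25% does not apply.

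**3. Raw contrast.** If the expected stress minus non-stress difference is zero at 0 and +30, those terms add nothing to the mean. AUC 0-150 and AUC 30-150 then have the same expected contrast in concentration × min. Only the variance differs.

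**4. Two reference cases for truncation.**
- Visit differences of equal SD, independent across samples: variance is proportional to the sum of squared weights, 3037.5 for 0-150 and 2362.5 for 30-150. Ratio of standardised effects: √(3037.5/2362.5) = 1.13.
- Visit differences almost perfectly correlated: variance is proportional to the squared sum of weights, so the ratio tends to 150/120 = 1.25.

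**5. Other assumed patterns** (standardised effect relative to total AUC 0-150):

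| Assumed pattern of visit differences | AUC 30-150 | AUC 30-150 adjusted for 0 and +30 differences |
|---|---|---|
| Correlation exp(−lag/τ), τ 30-120 min, fasting SD 0.4-1.0 of later SD | 1.12-1.21 | 1.22-1.80 |
| As above, +30 SD 0.6-0.8 and fasting SD 0.4 of later SD | 1.07-1.13 | within 1.1-1.8 |
| Early and late differences negatively correlated (damped cosine) | 0.99-1.11 | about 1.1 or more |

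The first row also assumes a stress effect of 1 unit at 45-90 min, fading to 0.25 at 150 min. Strong exchangeable correlation would put the adjusted gain above 1.8; that should not be relied on.

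**6. What this means for power.** Take the truncation factors 1.13 to 1.25.
- If 0.44 SD describes AUC 0-150, AUC 30-150 has power of about 0.88-0.94.
- If 0.44 SD describes the post-task response, AUC 0-150 has 0.44/1.13 = 0.39 to 0.44/1.25 = 0.35 SD, and power of about 0.69-0.61.
- With a factor of 1.0, power stays at 0.795.

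**The case against.** Four arguments stand against a stronger claim, and each largely succeeds.

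*The window is not stated.* A reader might infer that the outcome is an AUC over the whole visit. One value per visit is not an integration window, and an incremental AUC is equally compatible with the text. The 25% is therefore conditional. What stands without any condition is that the AUC is undefined and that no pre-task value enters the contrast.

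*Stress might act before +30.* A reader might infer that the early samples cannot respond to the task. C.6.2 has women appraise the upcoming task, and under C.6.3 visit 2 always uses the other paradigm, so anticipation is possible. C.2 can also be read as an earlier task start. If anticipation is real, adjusting for +30 removes part of the effect.

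*Nothing is biased.* A reader might infer that the stress effect is diluted, or that a chance early difference passes as a stress effect. Task order is randomised (C.6.7), and chance visit differences are part of the paired test's error term. The raw contrast and type I error are unaffected, and the power figure is not wrong on this account.

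*Whole-meal AUC is a legitimate outcome, and truncation may gain nothing.* The hypothesis concerns the postprandial response, and under negative early-late correlation the gain from truncation alone is about zero. Against an incremental AUC, unadjusted truncation can even lose precision.

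The case for adjustment survives this last argument. Total and incremental AUCs are both the same post-task sum plus fixed coefficients on the fasting and +30 values. Regression on those two differences estimates the variance-minimising coefficients, so in large samples it is no less efficient than either.

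**Conclusion.** The point holds as one of definition and precision. The AUC window and type are not specified, and the two pre-task samples have no role in the stress contrast. If a total AUC over 0-150 min is intended, those samples carry 25% of the weight and, absent anticipation, contribute variance only.

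The size of the loss cannot be derived from the documents. Over the assumed correlation patterns, truncation to 30-150 min raises the standardised effect by about 0-25%, and truncation with adjustment for both pre-task differences by about 10-80%. The adjusted analysis gained in every pattern examined; truncation alone did not. The analysis as written is not invalid, but the change is worth making.

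The difference between C.2 and C.6.2 on task timing is a separate inconsistency. It matters here because the description of 0-30 min as pre-task rests on C.6.2.

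**What to change.** In C.6.6 and the SAP:

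1. Define the AUC: total or incremental, integration rule, start and end, and whether time zero is the start or the end of the meal.
2. Analyse the stress contrast on the AUC from +30 to +150 min. Regress each woman's stress minus non-stress AUC difference on her stress minus non-stress differences in both the fasting and the +30 value, and read the effect at zero covariate difference.
3. Keep AUC 0-150 as a secondary outcome.
4. Report the pre-task difference by condition separately, so that any anticipatory effect is visible.
5. State which AUC the 0.44 SD refers to.
6. Reconcile C.2 with C.6.2 on when the task occurs relative to the meal. The window in item 2 takes +30 as the last pre-task sample and must follow whatever timing is confirmed.

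Cost: wording only, with no new samples or visits. Two covariates leave 40 − 3 = 37 residual degrees of freedom per meal group instead of 39. The primary AUC is no longer the whole-meal AUC, and adjusting for +30 could remove part of any anticipatory effect; items 3 and 4 are there to cover this.

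### Exploratory Aim 1b leaves out FFA, gives the fasting HOMA-IR and Adipo-IR no role, and compares mean AUC where C.1 predicts a stress-by-meal difference

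*Protocol*

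**What the plan says.** Protocol C.1 states the working hypothesis in two parts. The first is that "acute psychosocial stress will exacerbate the postprandial plasma glucose/insulin and free fatty acid (FFA) response to a standardized meal". The second is that "this response will be exaggerated after consumption of a high GI versus a low GI meal". The second part refers back to the first, so it covers FFA as well as glucose and insulin.

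Protocol C.6.2 places the fasting draw ahead of both meal and task: "A fasting blood and saliva sample will be collected immediately prior to consumption of the assigned standardized breakfast meal". C.6.6 then says that "HOMA-IR will be computed from fasting glucose and insulin values" and "Adipo-IR from fasting insulin and FFA values", and that the glucose/insulin and FFA AUCs "will be determined for each visit". Neither index is mentioned again in the Protocol. Neither appears in the SAP as outcome, covariate, stratifier or descriptive variable.

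For Aim 1b the SAP says that "an independent sample t-test will be employed to compare the mean" glucose/insulin AUC between the high-GI and low-GI groups. The aim is introduced as exploratory. It has no covariate, does not list FFA, and does not say outright which visit supplies the AUC, although its wording points to the stress visit. Aim 1a, the test described under Aim 2 and the Power Analysis all name AUC FFA; Aim 1b alone does not.

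**The concern.** Three gaps meet in one short paragraph of the SAP.

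- **Outcome.** The meal-type part of the FFA hypothesis has no planned comparison, although the data will exist.
- **Precision.** Aim 1b compares different women, so differences between women in insulin resistance go into its error term. The trial measures that characteristic before the meal and then assigns it no use. An index with no pre-specified role can also be brought in, or left out, after the results are seen.
- **Estimand.** C.1 predicts that the *effect of stress* is larger after the high-GI meal. Aim 1b compares mean AUC, which the meals can move with no stress effect at all: Table 1 gives 76% against 47% carbohydrate and 12% against 33% fat.

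At stake are the sharpness and interpretation of an exploratory comparison. The primary, within-woman stress contrast is not affected.

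**Working it through.** **Inputs.** 40 women per meal arm (Protocol C.2; SAP, Power Analysis). The SAP states about 80% power for 0.44 SD of the within-woman change. Alpha and sidedness are not stated; two-sided 0.05 is assumed throughout. The correlation r between a fasting index and AUC is not given; 0.1 to 0.7 is assumed. The documents do not say whether AUC is total or incremental.

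**1. The plan's own figure.** Paired comparison, normal approximation: power = Φ(0.44 × √40 − 1.960) = Φ(2.783 − 1.960) = 79.5%, which agrees with the stated 80%. The noncentral t with 39 df gives 77.4%. This figure covers the within-woman contrast only; Aim 1b has no power statement.

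**2. Aim 1b as written.** Two-sample comparison, 40 against 40:

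- Normal approximation: detectable difference = (1.960 + 0.842) × √(2/40) = 0.626 SD.
- Noncentral t, 78 df: 0.634 SD.
- Power at 0.44 SD: 49.3% (noncentral t).

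The SD here is the between-woman SD of AUC, not the SD of the change used in the Power Analysis.

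**3. Aim 1b adjusted for one fasting index.** The residual SD is multiplied by √(1 − r²), and one degree of freedom is spent (77 df). The equivalent gain in sample size is 1/(1 − r²).

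| Assumed r | √(1 − r²) | Detectable difference, 80% power | Equivalent women per arm, 40/(1 − r²) |
|---|---|---|---|
| none | 1 | 0.634 SD | 40 |
| 0.1 | 0.995 | 0.631 SD | 40.4 |
| 0.3 | 0.954 | 0.605 SD | 44.0 |
| 0.5 | 0.866 | 0.549 SD | 53.3 |
| 0.7 | 0.714 | 0.453 SD | 78.4 |

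For a true difference of 0.5 SD, unadjusted noncentrality is 0.5 × √(40/2) = 2.236, giving 59.8% power. At r = 0.5 it is 2.236/0.866 = 2.582, giving 72.2%.

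**4. What each comparison estimates.** Write the mean AUC after meal m as M(m) without stress and M(m) + S(m) with stress.

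- High minus low GI, stress-visit AUC: [M(high) − M(low)] + [S(high) − S(low)].
- High minus low GI, stress-minus-control change: S(high) − S(low).

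Only the second isolates the C.1 prediction. The first contains the plain meal effect, which can be non-zero when S(high) = S(low). This holds for glucose, insulin and FFA alike. The change-score comparison is again 40 against 40, so it too detects 0.634, but in SDs of the change.

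**The case against.** The strongest case against the point is that nothing in Aim 1b is wrong. Meal arm is randomised 1:1, so the unadjusted t-test is valid. The aim is exploratory, and an index may be computed merely to describe the sample. The gain rests on a correlation that the documents do not give: at r = 0.1 it is negligible, and it could be low if AUC is incremental. In women given the non-stress task first, the stress visit follows the wash-out, so a visit-1 index comes from a different day, which could weaken the correlation. If the change score is analysed, stable differences between women already cancel, and a fasting index helps only so far as it predicts the size of the stress effect. The FFA omission may be loose drafting, since the Power Analysis counts FFA as part of the metabolic response.

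Most of this stands, and it limits the point to a low-cost improvement. It does not remove it: Aim 1b names mean AUC without FFA, the indices have no stated role, and a loose outcome list still needs correcting before analysis.

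A reader might infer more than the documents support:

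- *That the t-test is biased.* Randomisation protects it in expectation.
- *That a substantial loss of precision is established.* It depends on an unknown r.
- *That FFA goes untested.* Its stress effect is tested in Aim 1a; only the meal-type contrast is missing.
- *That adding FFA to Aim 1b as written would test the C.1 hypothesis.* By step 4 of the working, a difference in mean AUC does not isolate it.

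**Conclusion.** The point holds as a minor one about precision and completeness. The textual parts need no assumption: Aim 1b omits FFA, uses no baseline, and compares mean AUC where C.1 predicts a difference in the stress effect, while HOMA-IR and Adipo-IR are assigned no use.

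The size of the precision gain is conditional on r, with two-sided 0.05 assumed. For the mean-AUC comparison it runs from practically nothing (0.634 to 0.631 SD at r = 0.1) to large (0.453 SD at r = 0.7); at r = 0.5, power for 0.5 SD rises from about 60% to 72%. These gains should not be carried over to the change-score comparison, where the covariate will probably add little.

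**What to change.** Amend the SAP, Aim 1b, as follows:

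1. Add AUC FFA to the outcomes.
2. Replace the t-test with a linear model of the stress-visit AUC on meal arm, adjusted for visit-1 fasting log HOMA-IR (glucose and insulin) or visit-1 fasting log Adipo-IR (FFA). The visit-1 value is preferred because no test meal or task can have affected it. This also gives both indices a stated role.
3. Also compare the within-woman stress-minus-control AUC change between meal arms for each outcome, and name this as the test of the C.1 stress-by-meal hypothesis.
4. State whether AUC is total or incremental.

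The cost is SAP wording, one degree of freedom per adjusted model, one more exploratory outcome, and a second comparison computed from the same data. No new samples, visits or participants are needed.
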